## 10. Final Power Assessment

Date conducted:

- Re-calculate power in the appropriate excel table, using the revised number of matched patients from the PS-match in Section 9. All other parameters in the table should be the same as in Section 8.
  - Pooled

| Superiority Analysis |             |
|-----------------------------|-------------|
| Number of patients matched  | 4,334       |
| Reference                   | 2,167       |
| Exposed                     | 2,167       |
| Risk per 1,000 patients     | 17.80       |
| Desired HR from RCT         | 0.44        |
| Alpha (2-sided)             | 0.05        |
|                             |             |
|                             |             |
| Number of events expected   | 77.1452     |
| Power                       | 0.950063363 |

- Optum CDM

| Superiority Analysis |             |
|-----------------------------|-------------|
| Number of patients matched  | 1,494       |
| Reference                   | 747         |
| Exposed                     | 747         |
| Risk per 1,000 patients     | 15.90       |
| Desired HR from RCT         | 0.44        |
| Alpha (2-sided)             | 0.05        |
|                             |             |
|                             |             |
| Number of events expected   | 23.7546     |
| Power                       | 0.516274582 |

- IBM® MarketScan®

| Superiority Analysis |             |
|-----------------------------|-------------|
| Number of patients matched  | 2,840       |
| Reference                   | 1,420       |
| Exposed                     | 1,420       |
| Risk per 1,000 patients     | 18.90       |
| Desired HR from RCT         | 0.44        |
| Alpha (2-sided)             | 0.05        |
|                             |             |
|                             |             |
| Number of events expected   | 53.676      |
| Power                       | 0.852553869 |

- Stop analyses until balance and final power assessment are reviewed by primary investigators, FDA, and assigned members of advisory board.

|  |              |                |            |
|--|--------------|----------------|------------|
| Reviewed by PI:                              | [name] | Date reviewed: | 04/16/2021 |
| Reviewed by FDA:                             | [name]   | Date reviewed: | 04/15/2021 |
| Reasons for stopping analysis (if required): |              |                |            |

## 11. Study Confidence and Concerns

Deadline for voting on study confidence and listing concerns:

Date votes and concerns are summarized:

- If final feasibility and power analyses are reviewed and approved, proceed to the remaining protocol steps.
- All study team and advisory board members that review this protocol should at this stage provide their level of confidence for the success of the RWD study in the [Google Form](#). This form also provides space for reviewers to list any concerns that they feel may contribute to a failure to replicate the findings of the RCT, including differences in study populations, poor measurement of study variables, or residual confounding. All responses will be kept confidential and individual-level results will only be shared with the individual respondent.
- After the deadline for voting has passed, provide the distribution of responses and summarize all concerns here.

## 12. Register study protocol on clinicalTrials.gov

Date conducted: 04/30/2021

- Register the study on [clinicalTrials.gov](#) and upload this document.

## 13. Comparative Analyses

Action report name:

Date conducted:

### 13.1 For primary analysis:

13.2 For sensitivity analyses:

## 14. Requested Results

14.1 Table 1: Baseline characteristics before and after adjustment

| Variable           | Before adjustment |          |            | After adjustment |          |            |
|--------------------|-------------------|----------|------------|------------------|----------|------------|
|                    | Referent          | Exposure | Std. diff. | Referent         | Exposure | Std. diff. |
| Number of patients |                   |          | -          |                  |          | -          |
| Age categories     |                   |          |            |                  |          |            |
| ...                |                   |          |            |                  |          |            |

14.2 Table 2: Follow-up time

| Patient Group              | Median Follow-Up Time (Days) [IQR] |
|----------------------------|------------------------------------|
| Overall Patient Population |                                    |
| Referent                   |                                    |
| Exposure                   |                                    |

14.3 Table 3: Censoring events

|  | Overall | Referent | Exposure |
|--|---------|----------|----------|
|  |         |          |          |

|                                 |  |  |  |
|---------------------------------|--|--|--|
| Outcome                         |  |  |  |
| Death                           |  |  |  |
| Start of an additional exposure |  |  |  |
| End of index exposure           |  |  |  |
| Specified date reached          |  |  |  |
| End of patient data             |  |  |  |
| End of patient enrollment       |  |  |  |
| ...                             |  |  |  |

14.4 Table 4: Results from primary analyses;

| Analysis   | No. exposed events | No. referent events | Exposed rate | Referent rate | HR (95% CI) |
|------------|--------------------|---------------------|--------------|---------------|-------------|
| Crude      |                    |                     |              |               |             |
| Analysis 1 |                    |                     |              |               |             |
| Analysis 2 |                    |                     |              |               |             |
| ...        |                    |                     |              |               |             |

HR, Hazard Ratio; CI, Confidence Interval.

14.5 Table 5: Results from secondary analyses.

## Appendix A

| # | VERO trial definitions  | Implementation in routine care   | Please see the following Google Drive for further details or any missing information:
https://drive.google.com/drive/folders/1WD618wrvvYIaxzflTcuK-VCnb6b-pV7usp-sharing   |  |
|---|---|--|--|--|
|   | Trial details - clinicaltrial.gov NCT01709110  |  | ICD-10 codes are not listed in this document because of excel cell size limitations and excessive number of ICD-10 codes. Full ICD-10 code lists will be available in the above Google Drive Folder (link above). ICD-9 to ICD-10 code conversions were completed using a SAS macro that implements forward/ backward mapping based on the CMS ICD-9 to ICD-10 mapping:
https://www.icer.org/data/icd9-icd-10-cm-and-pcs-crosswalk-general-equivalence-mapping.html |  |
|   | EXPOSURE vs. COMPARISON  |  | References/Rationale   | Color coding   |
| E | Exposure: 20 µg of teriparatide once daily   | Exposure: new use of Teriparatide (washout 730 days)

NDC Generic Name: TERIPARATIDE

NDC codes: 00002897101, 54868540600, 00002840001, 47781065289

Brand names: FORTEO

CPT/HCPGS Procedure Code: J3110   | Washout period - Criteria 20.1, 20.7   | Criteria   |
| C | Reference: 35 mg of oral risedronate once weekly

Aim: To compare the anti-fracture efficacy of teriparatide with risedronate in patients with severe osteoporosis  | Comparator: new-use of Risedronate (washout 180 days)

NDC Generic Name: RISEDRONATE SODIUM, RISEDRONATE SODIUM/CALCIUM CARBONATE

NDC codes: 00093309819, 00093309829, 00093309844, 00093309956, 00093310056, 00093550919, 00093550944, 00093777113, 00093777119, 00093777179, 00149047001, 00149047101, 00149047201, 00149047204, 00149047501, 00149047701, 00149047801, 00149047803, 0037840493, 00378411493, 00378415032, 00378415053, 00378471499, 00430047115, 00430047203, 00430047207, 00430047801, 00430047802, 00430097903, 005912040403, 00591204454, 00591207504, 00591207539, 00591210230, 00591210930, 00591387604, 16590072104, 16714087002, 23490924500, 33342010707, 33342010937, 33342010950, 47335066862, 47335066868, 47335092860, 47335092867, 49999044804, 54569546200, 54868438600, 54868467100, 54868551800, 54868606900, 59762040504, 59762040505, 59762040601, 59762040603, 59762040704, 60505309702, 60505309704, 60505316500, 63304044009, 63304044011, 65862051730, 65862051904, 65862051908, 65862087003, 65862087011, 68115068104

Brand names: ACTONEL, ATELVIA   |  | Adequate mapping in claims                                     |
|   | PRIMARY OUTCOME  |  |  | Intermediate mapping in claims                                 |
|   | New radiographic vertebral fractures during a 24-month study period.

[Lateral spine radiographs were repeated at 12 and 24 months or early termination for new vertebral fractures. Additional unscheduled radiographs were done at any interim visit to detect new clinical vertebral fractures if the patient reported back pain clinically suggestive of a vertebral fracture.] | Measured 1 day after drug initiation:

Vertebral Fractures:
Algorithm include the following case-qualifying (CQ):

CQ = 1 Inpatient claim with primary diagnosis code
ICD9 dx: 805.x, 806.x, 733.13
ICD10 dx: S12.0xxA, S12.0xxB-S12.6xxA, S12.6xxB, S12.S22.0xxA, S22.0xxB (excluding "traumatic" and "burst" fractures which are high-energy fractures), M48.50XA, M80.08XA(excluding "stress" and "fatigue" fractures)
OR
CQ = 2 Non-inpatient claim with any diagnosis code [ICD9 dx: 805.x, 806.x, 733.13; ICD10 dx: S12.0xxA, S12.0xxB-S12.6xxA, S12.6xxB, S12.S22.0xxA, S22.0xxB (excluding "traumatic" and "burst" fractures), M48.50XA, M80.08XA(excluding "stress" and "fatigue" fractures)] AND procedure code HCPGS (22305, 22310, 22315, 22318, 22319, 22325-22328, 22510-22515, 22520-22525, 27200, 27202, 72291, 72292, 76012, 76013, 77082, 77085, 77086, S2360-S2363)
OR
CQ = 3 Non-inpatient claim with diagnosis code [ICD9 dx: 805.x, 806.x, 733.13; ICD10 dx: S12.0xxA, S12.0xxB-S12.6xxA, S12.6xxB, S12.S22.0xxA, S22.0xxB (excluding "traumatic" and "burst" fractures), M48.50XA, M80.08XA(excluding "stress" and "fatigue" fractures)] AND Physician E&M codes (HCPGS: 99024, 99058, 99201-99215, 99241-99245, 99271-99285, 99301-99335, 99366, 99385-99387, 99395-99404, 99429, 99449) AND, up to 10 days earlier (or on the same day), Outpatient claim of spine imaging codes (HCPGS: 72010-72159, 72240-72285, 72295) [] | Wright NC, Daigle SG, Melton ME, Delzell ES, Balasubramanian A, Curtis JR. The Design and Validation of a New Algorithm to Identify Incident Fractures in Administrative Claims Data. J Bone Miner Res. 2019 Oct;34(10):1798-1807. doi:10.1002/jbm.3807. Epub 2019 Aug 5. PMID: 31170317.  | Poor mapping or cannot be measured in claims                   |
|   | INCLUSION CRITERIA   |  |  | Can't be measured in claims but not important for the analysis |
| 1 | Postmenopausal women ≥ 45 years of age at the time of entry into the trial, whose last menstrual period occurred at least 2 years prior to entry into the trial, and are sufficiently mobile to complete study visits.  | Female, ≥ 45 years of age at the time of drug initiation   |  |  |
| 2 | Women < 55 years of age in whom a bilateral oophorectomy cannot clearly be documented must have their postmenopausal status confirmed by a serum FSH level > 40 IU/L and serum estradiol level < 20 pg/mL or < 73 pmol/L.   | Measured 180 days prior to and including day of drug initiation in inpatient or outpatient care setting (any diagnosis position):

Excluded if patients had pregnancy codes Pregnancy (see "Pregnancy codes")  |  |  |

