### 5.3 Flowchart of the study cohort assembly

For teriparatide vs. risedronate

|  | Optum CDM         |                    | IBM® MarketScan®  |                    |
|--|-------------------|--------------------|-------------------|--------------------|
|  | Excluded Patients | Remaining Patients | Excluded Patients | Remaining Patients |
| All patients   |                   | 78202636           |                   | 200203908          |
| Did not meet cohort entry criteria   | -77830806         | 371830             | -199450502        | 753406             |
| Excluded due to insufficient enrollment  | -90897            | 280933             | -176733           | 576673             |
| Excluded due to prior use of referent  | -199055           | 81878              | -403827           | 172846             |
| Excluded due to prior use of exposure  | -19897            | 61981              | -44254            | 128592             |
| Excluded because patient qualified in >1 exposure category   | 0                 | 61981              | 0                 | 128592             |
| Excluded based on Inclusion criteria #1 - Age >= 45  | -1814             | 60167              | -3865             | 124727             |
| Excluded based on Inclusion criteria #2 - Female   | -4439             | 55728              | -9140             | 115587             |
| Excluded based on Inclusion criteria #3.1 - History of vertebral fracture (including from inception to 90 days)      | -48548            | 7180               | -103348           | 12239              |
| Excluded based on Inclusion criteria #3.2 - Vertebral fracture diagnosis excluded in the 90 days before cohort entry | -740              | 6440               | -969              | 11270              |
| Excluded based on Inclusion criteria #4 - Osteoporosis   | -3                | 6437               | -18               | 11252              |
| Excluded based on Exclusion criteria #1 - Pregnancy  | -1                | 6436               | -1                | 11251              |
| Excluded based on Exclusion criteria #2 - Paget's Disease  | -5                | 6431               | -9                | 11242              |
| Excluded based on Exclusion criteria #3.1 - Renal Osteodystrophy   | -2                | 6429               | -1                | 11241              |
| Excluded based on Exclusion criteria #3.2 - Osteomalacia   | -11               | 6418               | -12               | 11229              |

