| Risk per 1,000 patients | 15.9             | 18.9                    | 17.8          |

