## Appendix A

|  |   |  |
|--|---|--|
| 2
A minimum of 2 moderate (S02) or 1 severe (S03) vertebral fragility fractures
[radiographic evidence of at least two moderate (ie, a reduction in vertebral body height of 26–40%) or one severe (more than 40% reduction) prevalent vertebral fragility fracture]   | 
Measured from enrollment to 90 days prior to the day of drug initiation in inpatient or outpatient care setting (any position):
 
Vertebral Fractures diagnosis:
ICD9 diagnosis codes: 805.x, 806.x, 733.13
ICD10 diagnosis codes: M48.4, M48.5, M80.x, S12.x, S22.x, S32.x
 
Vertebral fracture procedures:
HCPCS codes: 22305, 22310, 22315, 22318, 22319, 22325–22328, 22510–22515, 22520–22525, 27200, 27202, 72291, 72292, 76012, 76013, 77082, 77085, 77086, S2360–S2363
ICD10 px: OPQ3xx, OPQ4xx, OPR3xx, OPR4xx, OPS3xx, OPS4xx
ICD-9 px: 03.53
  | 
NB. We excluded patients with diagnosis of vertebral fractures from 89 days prior to and including the day of drug initiation to increase the probability of measuring incident vertebral fractures and not prevalent vertebral fractures. The 90-day gap is described in: Wright NC, Daigle SG, Melton ME, Delzell ES, Balasubramanian A, Curtis JR. The Design and Validation of a New Algorithm to Identify Incident Fractures in Administrative Claims Data. J Bone Miner Res. 2019 Oct;34(10):1798–1807. doi: 10.1002/jbmr.3807.
 |
| 3
AP lumbar spine or total hip or femoral neck BMD $\geq$ 1.5 SD below the average BMD for young healthy, non-Hispanic, Caucasian women (T-score $\leq$ –1.5 SD).   | 
Measured start of all available data and including day of drug initiation in inpatient or outpatient care setting (any diagnosis position):
 
Osteoporosis diagnosis
ICD-9 diagnosis: 733.00, 733.01, 733.02, 733.03, 733.09, 733.13
ICD-10 diagnosis: M81.0, M81.6, M81.8, M80.88*, M80.00*, M80.01*, M80.02*, M80.03*, M80.04*, M80.05*, M80.06*, M80.07*, M80.08*
 
OR
 
Osteoporosis treatments:
Alendronate, Ibandronate, Risedronate, Etidronate, Tiludronate, Denosumab, Calcitonin, Romosozumab, Raloxifene, ZA, Pamidronate (reported as osteoporosis drug in the VERO trial)
  |  |
| 4
Without language barrier, cooperative, able to come to the clinic for all follow-up visits; has given informed consent before entering the study and after being informed of the medications and procedures to be used in this study.   | N/A   |  |

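### Under ICD-9 the primary outcome cannot separate a new vertebral fracture from continuing care of an old one, and the 90-day fracture-free gap is stated only at cohort entry

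*Combined protocol and SAP*

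**What the plan says.** Appendix A defines the primary outcome by three alternative case-qualifying rules.

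- **CQ1:** an inpatient claim with the fracture as primary diagnosis.
- **CQ2:** a non-inpatient diagnosis together with a listed procedure code.
- **CQ3:** a non-inpatient diagnosis together with a physician visit code and, "up to 10 days earlier (or on the same day), Outpatient claim of spine imaging codes". Its code list begins "CQ = 3 Non-inpatient claim with diagnosis code [ICD9 dx: 805.x, 806.x, 733.13; ICD10 dx: S12.0xxA, S12.0xxB-S12.6xxA, S12.6xxB".

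All three rules use the same ICD-9 codes. The outcome is "Measured 1 day after drug initiation", and the cell states no look-back from the candidate event.

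The fracture-history criterion in Appendix A lists the same ICD-9 diagnosis codes, from enrollment to 90 days before drug start. A note there excludes women with a vertebral-fracture diagnosis from day -89 to day 0, "to increase the probability of measuring incident vertebral fractures and not prevalent vertebral fractures". The Section 5.3 flowchart shows this as an entry step: "Vertebral fracture diagnosis excluded in the 90 days before cohort entry".

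Section 13.2, for sensitivity analyses, has a heading and no content.

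**The concern.** The question is whether teriparatide reduces new vertebral fractures relative to risedronate. The cohort is selected for earlier vertebral fracture, so old fractures are there to be coded again during follow-up. The plan regards a recent fracture code as a threat to incidence before drug start, yet it states no corresponding rule afterwards.

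Care of an old fracture is not a new event that either drug could have prevented. If such claims are counted equally often in both arms, they pull the hazard ratio toward 1 and lower power. If visits or spine imaging on treatment differ between arms, the error could go either way, and matching on baseline covariates would not correct it. In either case, a result that departs from the trial's 0.44 could not be told apart from outcome misclassification.

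**Working it through.** **1. The code lists side by side (Appendix A)**

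| | Required history | Outcome |
|---|---|---|
| ICD-9 diagnoses | 805.x, 806.x, 733.13 | 805.x, 806.x, 733.13 |
| ICD-10 diagnoses | M48.4, M48.5, M80.x, S12.x, S22.x, S32.x | legible codes all end in A or B |
| 90-day gap | day -89 to day 0 | none stated |

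The plan narrows the outcome list in one coding system and not in the other.

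**2. What the stated rules do with a sequence of claims**

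- An old fracture is coded at a plain visit on day 40. There is no imaging and no listed procedure, so it is not an event.
- The same fracture is coded on day 100 at a visit with spine imaging. CQ3 is met and it counts as new, although a fracture code appeared 60 days earlier.
- An old fracture is first coded again at an imaged visit. It counts as new, and the entry exclusion guarantees at least 90 diagnosis-free days before it.

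**3. The plan's power figure (Section 10)**

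Events D = 4,334 × 17.80/1,000 = 77.1452. Power = Φ(√D × |ln HR|/2 − 1.960) = Φ(8.783 × 0.8210/2 − 1.960) = Φ(1.645) = 0.950, as stated. The same formula gives 0.516 for Optum and 0.853 for MarketScan, also as stated. The power arithmetic is sound.

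**4. Exposure to the ICD-9 rule (Appendix B, matched, pooled, both arms)**

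- 2004–2006: 194 + 192 = 386
- 2007–2009: 419 + 415 = 834
- 2010–2012: 560 + 550 = 1,110
- 2013–2015: 559 + 561 = 1,120
- 2016 onward: 435 + 449 = 884

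Entries to 2012 are 2,330/4,334 = 53.8%. Entries to 2015 are 3,450/4,334 = 79.6%. The documents do not give the date of the coding switch, so these two figures serve as a bracket.

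**5. Sensitivity to an assumed false share**

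Let f be the share of all counted events that are old-fracture care, equally frequent in both arms, with HR 0.44 for true events.

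Observed HR = [0.44(1−f)/1.44 + f/2] / [(1−f)/1.44 + f/2]

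At f = 0.20 this is (0.2444 + 0.1)/(0.5556 + 0.1) = 0.525. Power uses the formula in step 3. The last column removes all false events and no true ones, which is the best case for any stricter definition.

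| f (assumed) | Observed HR | Power, 77.1 events | Power if only true events remain |
|---|---|---|---|
| 0% | 0.440 | 0.950 | 0.950 (77.1 events) |
| 10% | 0.481 | 0.894 | 0.928 (69.4) |
| 20% | 0.525 | 0.807 | 0.897 (61.7) |
| 30% | 0.572 | 0.689 | 0.855 (54.0) |

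Now confine the error to ICD-9 events, and spread events in proportion to entries. A false share of 20% among ICD-9 events means f = 0.108 to 0.159, an observed HR of 0.485 to 0.507, and power of 0.889 to 0.846. A false share of 30% means HR 0.508 to 0.543 and power 0.845 to 0.764.

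**6. What an ICD-10-era analysis could show**

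Assuming the pooled risk holds in each era, 884 × 17.80/1,000 = 15.7 events. Power at HR 0.44 is Φ(3.967 × 0.8210/2 − 1.960) = Φ(−0.33) ≈ 0.37.

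**The case against.** The case rules are real filters. A plain follow-up visit with neither imaging nor a listed procedure never qualifies, and CQ1 needs an inpatient primary diagnosis. The first fracture diagnosis in follow-up always comes after at least 90 diagnosis-free days, so a rolling gap acts only when an earlier non-qualifying code precedes the candidate claim. The gap can also drop a true fracture: one first coded on day 40 and imaged on day 55 falls outside CQ3's 10 days. All of this stands. It limits what the fix can do but does not remove the gap in the definition.

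Appendix A sends the reader to an external folder for further details, the ICD-10 string is garbled, and the outcome cell ends in an empty bracket. A per-event rule may exist elsewhere. The most that can be said is that none is stated in these documents.

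A reader might take the flowchart as a measure of the problem. After the history step, 740/7,180 women in Optum and 969/12,239 in MarketScan were removed for a diagnosis in the preceding 90 days, 1,709/19,419 = 8.8% pooled, against an outcome risk of 1.78%. The comparison is not like for like. The 8.8% carries none of the CQ filters, mixes new and old fractures, and describes women who were excluded. A low outcome risk fits effective filters as well as it fits contamination.

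**Conclusion.** The outcome as stated can count care of an old vertebral fracture as a new one. The weakness lies in the ICD-9 codes, which cover roughly 54% to 80% of matched entries, and in the absence of a stated per-event gap. This works against the plan's own aim of measuring incident fractures.

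The size is unknown. The hazard ratios and powers above rest on assumed false shares and on equal error in both arms. They show sensitivity and do not estimate bias. That A and B endings mark initial encounters, and that ICD-9 has no counterpart, are coding conventions and not statements in the documents.

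Three stronger readings are not supported:

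- **That old-fracture care is counted as a rule.** The filters block part of it, and no rate is given.
- **That the bias is certainly toward 1.** This needs equal error in both arms.
- **That every woman has a coded vertebral fracture.** The history criterion also lists procedure codes without saying whether they are an alternative to a diagnosis, and it uses whole ICD-10 groups such as M80.x, S22.x and S32.x.

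**What to change.** Before the comparative analysis:

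1. **Outcome definition, Appendix A.** Add that a CQ1–CQ3 claim counts only if no vertebral-fracture diagnosis, of any encounter type and from the outcome's anatomical sites, occurs in the 90 days before that fracture episode. State the episode window in days. It must be wide enough to keep a new fracture first coded at a plain visit and imaged soon after; CQ3's 10 days alone would lose the day-40/day-55 case. If such a rule already sits in the external folder, move it into the outcome definition.
2. **Reporting.** Give the primary result with and without the rule, with event counts by arm.
3. **Section 13.2.** Add a comparison by coding era, labelled descriptive because only about 16 events are expected among entrants from 2016 onward.

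The cost is one condition in the outcome code and two additional runs. Some true new fractures will be dropped and the event count will fall, so the Section 10 power should be recomputed. The rule does not remove old-fracture care that first recurs after 90 or more code-free days, and the protocol should state this as a remaining limitation.
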